Processing pipeline: Data will be motion corrected with our validated rt-fMRI motion correction algorithm[61]. Data cleaning will include linear and quadratic drift removal; regression of cerebrospinal fluid, white matter and global signals; calculation and removal of a 24-parameter motion model (6 motion parameters, 6 temporal derivatives and their squares)[62]; motion censoring[63]; and low-pass filtering via temporal smoothing with a Gaussian filter. Connectivity will be calculated using Pearson correlation. As connectivity is very sensitive to head motion[64], we include two types of motion censoring to remove confounding effects of motion on connectivity and the resulting feedback signal. For each frame, we will calculate the frame-to-frame displacement as defined in[64]. Frames with motion >0.15mm and the two frames immediately before and after (to account for temporal smoothing) will be excluded. We will also censor whole blocks of feedback if a large number of frames (e.g., 10%) have been censored. These features minimize the likelihood of subjects receiving feedback mainly reflecting motion artifacts. After calculating connectivity for all predefined nodes, edge strength for all connections in the predefined network will be summarized in the same manner as Step 2 in CPM (**see Connectome-based predictive modeling**, above)[31]. The feedback signal will be the overall strength of the opioid abstinence network. For data harmonization, imaging data collected at baseline and follow-up scans will be processed (off-line) in the same manner as the neurofeedback data.

Neurofeedback and transfer runs: Feedback and transfer runs will consist of 30 sec blocks during which subjects try to increase connectivity in the opioid abstinence network. During feedback runs, subjects in the active feedback group will be given feedback as the difference between positive and negative edges: feedback = $\sum_{edges} r(\text{positive edges}) - \sum_{edges} r(\text{negative edges})$. Feedback will be presented as a bar graph with hot colors for positive differences and cool colors for negative differences (similar to **Fig 1**). Subjects will be instructed to increase the feedback bar (i.e. increase overall network strength), as indicated by a green arrow pointing up for 30 sec, and feedback will be presented intermittently

IRB# 2000025618

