Aim 2: *To determine if connectome-based neurofeedback is associated with changes in intrinsic connectivity.* H2a. Subjects receiving active versus sham feedback will show increased opioid abstinence network connectivity between resting state acquired at follow-up versus baseline scans. H2b. This effect will generalize to increased connectivity during fMRI reward and cognitive tasks as in our pilot data.

Approach: Opioid abstinence network connectivity strength will be calculated during resting state (H2a), MIDT and Stroop tasks (H2b) as in our pilot data, and will be entered into a linear mixed effects model with the between-subject factor of feedback group (active/sham) and the within-subject factor of time (baseline/follow-up scans).

Aim 3: *To determine if connectome-based neurofeedback is associated with greater improvements in clinical features of OUD than sham feedback.* H3a. Subjects receiving active versus sham feedback will show reduced craving and negative affect at follow-up versus baseline scans. H3b. Increased opioid abstinence network connectivity during transfer runs will be correlated with reduced craving and negative affect.

Approach: Craving (Opioid Craving Scale) and negative affect (Quick Inventory of Depressive Symptomatology) will be calculated at follow-up and baseline scans and compared between groups using repeated measures analysis of variance. Change in opioid abstinence network connectivity strength will be calculated during transfer runs at baseline and follow-up scans. We will test for Pearson's correlations between change in connectivity strength and changes in craving and negative affect.

5. **Genetic Testing** N/A

6. **Subject Population:** Provide a detailed description of the types of human subjects who will be recruited into this study.

IRB# 2000025618

Write here

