We plan to enroll twenty-four individuals (12 male, 12 female) receiving methadone for OUD. Eligibility criteria: (i) non-methadone opioid positive urine screen (as assessed during standard treatment at APT) or indicated via Utox or self-reported past-month opioid use at screening); (ii) DSM-5 criteria for OUD, as assessed via structured clinical interview (SCID)[66]; (iii) ≥ 3 months of methadone treatment; (iv) eligibility for MRI; (v) age 18-50; (vi) baseline scanning with acceptable motion (i.e., <.15mm frame-to-frame displacement), as in prior work. Retention: APT patients attend clinic on a daily basis to receive methadone and this has contributed to high retention rates (e.g., 86% over three months) in our studies[10, 67] in this population.

7. **Subject classification:** Check off all classifications of subjects that will be specifically recruited for enrollment in the research project. Will subjects who may require additional safeguards or other considerations be enrolled in the study? If so, identify the population of subjects requiring special safeguards and provide a justification for their involvement.

 Children	 Healthy	 Fetal material, placenta, or dead fetus
 Non-English Speaking persons	 Prisoners	 Economically disadvantaged
 Decisionally Impaired fetuses	 Employees	 Pregnant women and/or
 Yale Students	 Females of childbearing potential	

NOTE: Is this research proposal designed to enroll children who are wards of the state as potential subjects?

Yes No

8. **Inclusion/Exclusion Criteria:** What are the criteria used to determine subject inclusion or exclusion?

Write here

- i. Inclusion criteria
 1. non-methadone opioid positive urine screen (as assessed during standard treatment at APT) or indicated via Utox or self-reported past-month opioid use at screening
 2. DSM-5 criteria for opioid use disorder, as assessed via structured clinical interview (SCID)
 3. ≥ 3 months of methadone treatment
 4. Age 18 to 50
- ii. Exclusion criteria
 1. Meet DSM-5 psychiatric classifications for lifetime schizophrenia or bipolar disorder with psychotic features, or exhibit significant current suicidal or homicidal plans and intent such that hospitalization is required

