 2. Failure to pass an MRI screening
 3. Women who are pregnant or nursing
 4. Baseline scanning with excessive motion based on frame-to-frame displacement

9. How will **eligibility** be determined, and by whom? *Write here*

Participants will be recruited via clinician referrals from the APT Foundation, one of the largest methadone providers in CT, consistent with our prior[10, 48] and ongoing work. In

IRB# 2000025618

addition to regular attendance for methadone, APT patients meet regularly with clinicians, as per federal guidelines. As [name] (Co-I) is Director of Research for the APT, he is ideally suited to facilitate participant referral and longitudinal clinical assessment for this study.

Individuals will be informed about the study by their clinician at their regular APT clinic visits and provided with verbal information and brochures containing project information. Interested individuals will contact the study team and set up a screening visit. At the screening visit, eligibility will be determined by members of the research team.

10. Risks: Describe the reasonably foreseeable risks, including risks to subject privacy, discomforts, or inconveniences associated with subjects participating in the research.

Write here

- i. Potential risks: This protocol presents minimal risks to subjects. Possible risks include:
 1. Magnetic resonance imaging: MRI is a non-invasive procedure with minimum anticipated discomfort and a safety screening process. Prior studies have not found any adverse effects of MRI. The possible risks and discomforts of MRI are as follows:
 - a. Claustrophobia
 - b. Acoustic noise
 - c. Metal implants are a risk within the magnetic MRI environment
 - d. Discomfort lying in the MRI scanner
 - e. Very slight warming of the body, tingling or involuntary muscle twitches
 - f. Unknown risk to a fetus
 2. Behavioral assessments: These are all non-invasive and should add no risk. The major disadvantage will be the time taken to complete the questionnaires. Our past experience with these and related measures indicates that they are acceptable to subjects including individuals with substance use disorders.
 3. Urine toxicology test and its result: This is non-invasive and should add no risk. Our past experience indicates that urine screens are acceptable to subjects including individuals with substance use disorders.

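### Low motion on the baseline scan is an entry condition, but the follow-up scan has no session-level limit and the Aim 2 model has no motion term, so a single-arm change in connectivity could partly reflect motion

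*Combined protocol and SAP*

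**What the plan says.** **Entry.** Section I, 6 (Subject Population, criterion vi) requires "baseline scanning with acceptable motion (i.e., <.15mm frame-to-frame displacement". Section I, 8 repeats this as an exclusion: "Baseline scanning with excessive motion based on frame-to-frame displacement". Neither place says whether the limit applies to a mean, a maximum or a share of frames. Neither mentions the follow-up scan.

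**Processing.** The processing pipeline in Section I, 4 gives its reason for censoring: "As connectivity is very sensitive to head motion". It then sets a frame rule, "Frames with motion >0.15mm and the two frames immediately before and after (to account for temporal smoothing) will be excluded", together with "calculation and removal of a 24-parameter motion model" and regression of the global signal. It also states that "imaging data collected at baseline and follow-up scans will be processed (off-line) in the same manner as the neurofeedback data".

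**Analysis.** Aim 2 compares network strength at rest (H2a) and during the two tasks (H2b) in a "linear mixed effects model with the between-subject factor of feedback group (active/sham) and the within-subject factor of time (baseline/follow-up scans". Section I, 13 repeats the same two factors. Motion is in neither version.

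**Design.** Section I, 1 and the study design paragraph of Section I, 4 put all 24 participants on active feedback. The hypothesis tests in Section I, 4 and the models in Section I, 13 compare active with sham, and Section I, 13 counts 12 per group.

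**The concern.** The baseline scan does two jobs: it is the motion screen and the reference for the pre-post comparison. People stay in because that particular session had low motion. Motion is not perfectly repeatable between sessions, so their expected motion at follow-up is higher even if nothing has changed. This is ordinary regression to the mean.

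Identical processing does not make unequal sessions equal. A session with more movement loses more frames, and any motion effect left after cleaning is larger. If all 24 receive active feedback, the group factor has one level and Aim 2 reduces to baseline versus follow-up. Nothing in the model then separates a motion shift from a training effect. H2a and H2b could show a change that is partly motion, or a true change could be masked.

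**Working it through.** **The plan's own figure.** Section I, 13 gives power 0.99 from noncentrality 5.36, critical t 2.10 and 18 df. A noncentral t at two-sided 5% gives critical t 2.101 and power 0.999, so the figure reproduces to within 0.01. It comes from prior work with 10 per group and has no motion input, so it does not bear on this point.

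**Inputs from the documents.** n = 24. Up to 40 scanned for 24 completers (Section III, 2). If every loss were a motion failure, the pass share is q = 24/40 = 0.60, the lowest value those planning figures allow. If the 86% retention in Section I, 6 also applies, 24/0.86 = 27.9 must pass, and q = 27.9/40 = 0.70.

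**Assumed inputs (the documents give none).** Motion on a suitable scale is bivariate normal across sessions, SD 1. Between-session correlation r is 0.4-0.8. Correlation b between motion and network score after processing is 0.1-0.4. Retest correlation of the score is 0.5.

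**Step 1, rise in motion.** With cut c = z(q), mean baseline motion among those admitted is -φ(c)/q, and at follow-up it is r times that. The rise is (1 - r)φ(c)/q. For q = 0.60, φ(0.253)/0.60 = 0.386/0.60 = 0.644; with r = 0.4 the rise is 0.6 × 0.644 = 0.386 SD.

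**Step 2, spurious change.** b × rise = 0.4 × 0.386 = 0.155 SD.

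**Step 3, false-positive rate.** The SD of change is √(2(1 - 0.5)) = 1, so noncentrality is 0.155 × √24 = 0.76. Against t(23) = 2.069, two-sided, the test rejects 11.2% of the time.

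| q | r | b | Rise (SD) | Spurious change (SD) | False-positive rate |
|---|---|---|---|---|---|
| 0.60 | 0.4 | 0.4 | 0.39 | 0.155 | 11.2% |
| 0.70 | 0.4 | 0.4 | 0.30 | 0.119 | 8.7% |
| 0.60 | 0.6 | 0.3 | 0.26 | 0.077 | 6.5% |
| 0.70 | 0.6 | 0.3 | 0.20 | 0.060 | 5.9% |
| 0.80 | 0.6 | 0.3 | 0.14 | 0.042 | 5.4% |
| 0.60 | 0.4 | 0.1 | 0.39 | 0.039 | 5.4% |
| 0.90 | 0.8 | 0.1 | 0.04 | 0.004 | 5.0% |

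For scale, a paired test with n = 24 has 80% power at a change of 0.60 SD. The largest spurious change in the table is about a quarter of that (0.155/0.60 = 0.26).

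**Step 4, a control arm and a covariate.** Simulated type I error, 20,000 runs per row. The group-by-time test is 12 versus 12. The adjusted test is the intercept of change in score regressed on change in motion. The last two rows go beyond the range above (b = 0.5, and retest 0.8 in the last) as a stress test.

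| q, r, b, retest | Time effect, unadjusted | Group-by-time | Time effect, adjusted |
|---|---|---|---|
| 0.9, 0.8, 0.1, 0.5 | 4.8% | 5.3% | 4.8% |
| 0.8, 0.6, 0.3, 0.5 | 5.3% | 4.9% | 4.9% |
| 0.6, 0.4, 0.5, 0.5 | 14.3% | 5.0% | 4.7% |
| 0.6, 0.4, 0.5, 0.8 | 22.9% | 5.1% | 4.9% |

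The adjusted model is correct by construction here, so the last column shows that the remedy works under these assumptions, not in general.

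**Step 5, retained data.** A 10-minute run at TR 2 s has 300 frames. Each isolated frame over the limit removes up to 5, or 1.7% of the run. The same rule therefore leaves less data in the session with more movement.

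**Step 6, a matched limit.** Applying the entry cut at follow-up would remove 24 × P(over at follow-up given under at baseline): about 1.2 participants at q = 0.9, r = 0.8, and 7.1 at q = 0.6, r = 0.4.

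**The case against.** The case against is substantial, and much of it limits the point.

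- **Motion is controlled at follow-up.** A reader might infer from the entry criterion that follow-up motion is unchecked. The documents do not support that: the 0.15 mm frame rule and the motion regression cover both scans. The score is also positive minus negative edges, so motion effects common to both sets partly cancel. This stands, and only a remainder is at issue.
- **The bias may be small.** If half of those scanned failed on motion, with r = 0.4 and b = 0.4, the rate would be 14.7%. But 24 of 40 implies that at least 60% pass, and the plan attributes the surplus scans to attrition. If b is 0.1 or less, the rate stays at 5.0-5.4%.
- **The net direction is open.** Mock-scanner exposure and three training scans precede follow-up, so habituation could offset the rise. If motion lowers the score, the bias works against H2a. A reader might infer that a positive H2a result would probably be false; nothing in the documents supports that.
- **The model as written has a sham arm.** Selection acts equally on both arms, so group-by-time is not inflated (4.9-5.3%). That is correct, but Section I, 1 and the study design paragraph describe no sham arm. The point holds for the all-active design only.
- **H3b.** A reader might extend the point to H3b because it uses change in connectivity. Adding a constant to every change score leaves a Pearson or Spearman correlation unchanged, so a uniform shift does not bias it. Bias would need each person's motion change to track their change in craving or affect, and the documents give no sign of that.

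What remains is narrow: in a single-arm pre-post comparison, equal processing does not guarantee equal residual motion, and nothing in the analysis would show the difference.

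**Conclusion.** The point holds as a modest, conditional weakness of the single-arm Aim 2 time effect (H2a and H2b). The textual facts are secure: entry is selected on baseline motion, follow-up has no session-level limit, and the model has no motion term.

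The size rests on assumptions. With at least 60% passing the entry limit, residual correlation up to 0.4 and retest correlation 0.5, the false-positive rate is about 5-11%. Mid-range inputs give about 5-6.5%, and effective cleaning makes the excess negligible. Higher figures need every input at an extreme. The sign of the bias cannot be determined from the documents. The point does not reach H3b or a true active-versus-sham group-by-time contrast. It is worth acting on because the remedy is cheap, not because the expected distortion is large.

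**What to change.** - Add run- or session-level mean frame-to-frame displacement as a time-varying covariate in the H2a and H2b models, and report the unadjusted result alongside. The pipeline already computes frame displacement.
- Tabulate displacement and retained frames at baseline and follow-up.
- State which summary of displacement the entry limit refers to, and add a sensitivity analysis that applies the same limit to follow-up scans.
- Reconcile the all-active description with the active/sham hypotheses, models and 12-per-group count, since the design decides whether this bias can arise.

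No new data are needed. The covariate costs one degree of freedom and could remove some true effect if training itself changes motion, which is why both results should be shown. The matched-limit analysis would lose about 1-7 of 24 participants, so it should stay a sensitivity analysis.

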Connectome-based neurofeedback can be used to target clinically-relevant brain networks: Both connectome-based models of behavior and real-time fMRI (rt-fMRI) feedback are novel techniques at the cutting-edge of neuroimaging methodology. Functional connectivity patterns are unique to each individual and contain information about each individual’s behavior, such that generalizable models can be constructed to predict behavior in novel subjects—for example, as implemented using CPM. Rt-fMRI is a non-invasive, non-pharmacological tool that enables an individual to learn to modulate their brain activity. It thus enables concurrent assessment of brain activation patterns related to specific functions, and of individual abilities to regulate such functions. However, prior rt-fMRI research in addictions and other disorders have not focused on functional connectivity, but have primarily provided feedback based on activation patterns in a single brain region. In contrast, connectome-based neurofeedback is based on network-level patterns of functional connectivity. Predictive brain networks can then be targeted in an individual using rt-fMRI neurofeedback to modify brain dynamics. *To improve understanding of mechanisms of opioid relapse, this project will use connectome-based neurofeedback to target the previously identified opioid abstinence network.*

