Task fMRI (MIDT, Stroop)	X		X	
Behavioral (craving, affect)	X	X	X	X

Connectome-based predictive

modeling (CPM): We have developed and applied CPM to predict complex behavioral phenotypes in healthy and clinical populations[11, 12, 30, 45-47] including methadone populations[10]. CPM is a data-driven method for generating predictive models of brain-behavior relationships from functional connectivity matrices using cross-validation[11, 30, 31, 45], developed by members of the investigative team (MPI [name]). This approach has been validated in several studies^{e.g.,[11, 30, 45]}. CPM is composed of the following steps: (1) edge selection, in which linear regression is used to relate each edge (correlations between node pairs in the matrix) in the connectome to a behavioral variable of interest (e.g., opioid use) in the training dataset; (2) edge summarization, in which weights of edges identified in Step 1 are summed to create a single summary value for each subject; (3) model building, in which summary scores (the independent variable) are linearly related to the behavioral variable (the dependent variable); (4) model application, in which resultant coefficients from Step 3 are applied to novel connectomes in the testing dataset to generate behavioral predictions; and (5) model evaluation, in which the predictive ability of the CPM is evaluated using either mean squared error or the correlation between predicted and observed behavioral values. Testing models on independent samples ensures that models do not over-fit a specific dataset; rather they generalize and will likely replicate in future work^{e.g.,[11, 30, 45]}. We previously used CPM to predict cocaine abstinence during a 12-week treatment using task data from individuals scanned prior to treatment for cocaine-use[10]. CPM successfully predicted abstinence during treatment (% negative urines) ($p=0.002$). To determine the generalizability of our findings, we tested the ability of the identified networks to predict cocaine-negative urine toxicology outcomes in a separate, heterogeneous sample of cocaine-dependent individuals ($n=45$). Network strength in this independent sample also predicted abstinence during treatment ($p=0.016$)[10]. More recently, we have used CPM to identify a neural network predictive of opioid use among individuals receiving methadone for OUD (Yip et al., In Prep). As with the cocaine network, this network was robust and was not significantly altered in follow-up analyses controlling for other baseline clinical variables including past-month opioid-use or methadone dose. Further consistent with prior CPM work[10, 11, 30, 45], the opioid network was complex and composed of multiple adjacent and nonadjacent nodes with varying degrees of connectivity (i.e., high- versus low-degree nodes). *These data demonstrate the ability of CPM to identify complex neural networks subserving specific addiction outcomes that replicate in independent samples.*

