The statistical tests will be as follows: Aim 1: Opioid use will be entered into a linear effects model with the between-subject factor of feedback group (active/sham). Aim 2: Opioid abstinence network strength during resting state and task fMRI runs will be compared between time points using linear mixed models with the between-subject factor of group (active/sham) and the within-subject factor of time (baseline/follow-up scan). Aim 3: Craving and negative affect will be compared using linear mixed effects model with the between-subject factor of group (active/sham) and the within-subject factor of time (baseline/follow-up scan). Associations between craving and negative affect and opioid abstinence network connectivity strength during transfer runs will be tested using Pearson's or Spearman's correlations, as appropriate depending on the distribution of the data. Replication: For replication of our pilot data (Figure 2 of research strategy), Pearson's correlations will be tested between opioid abstinence network connectivity strength at baseline and percent opioid-negative urines across the study.

SECTION II: RESEARCH INVOLVING DRUGS, BIOLOGICS, RADIOTRACERS, PLACEBOS AND DEVICES

If this section (or one of its parts, A or B) is not applicable, check off N/A and delete the rest of the section.

A. RADIOTRACERS N/A

B. DRUGS/BIOLOGICS N/A

C. DEVICES N/A

SECTION III: RECRUITMENT/CONSENT AND ASSENT PROCEDURES

1. Targeted Enrollment: Give the number of subjects:

- a. Targeted for enrollment at Yale for this protocol:
24 completers (individuals participating in all scanning sessions).
- b. If this is a multi-site study, give the total number of subjects targeted across all sites: NA

2. Indicate recruitment methods below. Attach copies of any recruitment materials that will be used.

 Flyers	 Internet/web postings	 Radio
 Posters	 Mass email solicitation	 Telephone
 Letter	 Departmental/Center website	 Television
 Medical record review*	 Departmental/Center research boards	 Newspaper
 Departmental/Center newsletters	 Web-based clinical trial registries	 Clinicaltrials.gov

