 YCCI Recruitment database	 Social Media (Twitter/Facebook):	
 Other:		

IRB# 2000025618

We plan to collect full data from twenty-four individuals (12 M, 12 F) receiving methadone for OUD. Thus, in order to account for possible participant attrition, we will likely scan up to 40 individuals (and anticipate screening up to 100). Participants will be recruited via clinician referrals from the APT Foundation, one of the largest methadone providers in CT, consistent with our prior[48, 49] and ongoing work. While rates of other forms of medication-assisted treatment (e.g., buprenorphine, naltrexone) have increased in recent years, methadone remains the most prevalent treatment for OUD in the US[20], therefore, to reduce sample variability, this study will only recruit individuals treated with methadone. For regular attendance for methadone, APT patients meet regularly with clinicians, as per federal guidelines. [name] (Co-I), Director of Research for APT, is ideally suited to facilitate participant referral and longitudinal clinical assessment for this study.

* Requests for medical records should be made through JDAT as described at
<http://medicine.yale.edu/ycci/oncore/availableservices/datarrequests/datarrequests.aspx>

3. Recruitment Procedures:

- a. Describe how potential subjects will be identified. *Write here*
- b. Describe how potential subjects are contacted. *Write here*
- c. Who is recruiting potential subjects? *Write here*

Consistent with previous studies conducted by the PI and co-investigators, participants in methadone treatment for an opioid-use disorder will be recruited from the APT Foundation. Interested participants entering the methadone treatment program at APT will be referred by APT personnel to research staff when possible for eligibility screening. [name], a co-investigator for this study, is both the Director of Research and the Director of Pain Services for the APT Foundation, he is ideally suited to facilitate participant referral and longitudinal clinical assessment for this study. Participants may also be referred to the study by word of mouth from other participants. HIC approved recruitment materials will provide information about how to contact research staff to learn more about the study. All recruitment will be conducted by local HIC-approved study personnel who completed HIC training requirements.

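### The planned replication of the opioid abstinence network is not restricted to people outside the sample that produced the network, so its independence is not secured (minor).

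*Combined protocol and SAP*

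**What the plan says.** **Recruitment.** Section I, item 9 describes the source of participants as follows: "recruited via clinician referrals from the APT Foundation, one of the largest methadone providers in CT, consistent with our prior[10, 48] and ongoing work". Section III, item 3 repeats this: "Consistent with previous studies conducted by the PI and co-investigators, participants in methadone treatment for an opioid-use disorder will be recruited from the APT Foundation". It adds two referral routes: "Interested participants entering the methadone treatment program at APT will be referred by APT personnel to research staff when possible for eligibility screening", and "Participants may also be referred to the study by word of mouth from other participants".

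**Eligibility.** Section I, item 8 requires OUD, recent non-methadone opioid use, age 18 to 50, and "≥ 3 months of methadone treatment" with no upper limit. The exclusions there concern psychiatric state, MRI screening, pregnancy or nursing, and head motion. Item 11 adds claustrophobia and metal implants. Nothing in items 6, 8, 9 or 11 mentions earlier participation in the team's studies.

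**The network.** Section I, items 1 and 3 present it as fixed in advance. It comes from the team's own connectome-based predictive modeling (CPM) in methadone-maintained people with OUD, with two scanning sessions 3 months apart. The source is cited as in preparation.

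**The analysis.** Section I, item 13 states: "For replication of our pilot data (Figure 2 of research strategy), Pearson's correlations will be tested between opioid abstinence network connectivity strength at baseline". The other variable in the correlation is the share of urine samples that are negative for opioids over the study. No analysis set is named for it.

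**The concern.** The protocol sets its own standard in the CPM paragraph of Section I, item 3: "Testing models on independent samples ensures that models do not over-fit a specific dataset". The same item says: "Functional connectivity patterns are unique to each individual and contain information about each individual’s behavior". Together these mean that a person who helped to build the network is not an independent test case for it, even with a new scan and new urine results. Edges selected because they matched that person's connectome and opioid use will partly match again on re-measurement, whether or not the network holds in anyone else.

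At stake is the meaning of a positive replication. With 24 participants and no record of who was in the derivation sample, a reader could not tell validation in new people from re-measurement of old ones.

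**Working it through.** **The plan's own figure.** Item 13 gives no power or sample size for the replication. Its only reproducible figure is the two-group power: noncentral t, df = 18, δ = 5.36, critical t = 2.10. This gives 0.999, consistent with the stated 0.99. The present point does not depend on it.

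**Step 1: can a derivation participant enter?**
- Eligibility: no rule prevents it, and long-term methadone patients qualify.
- Source: this trial uses the provider used for the team's earlier studies. Item 6 reports 86% three-month retention of this provider's patients in the team's studies, and item 13 reports more than 85% in fMRI studies of methadone patients. The team has therefore already scanned people from this kind of population.
- Not stated: where the derivation sample was recruited, how many people it had, and whether any of them could still be eligible.

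Overlap is possible, but the documents do not establish it.

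**Step 2: threshold for the replication.** For n = 24, the two-sided 5% critical value is r = t/√(n − 2 + t²) with t = 2.074, so r = 2.074/√(22 + 4.301) = 0.404.

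**Step 3: illustrative size.** A network with no true validity was simulated. None of the following assumptions is in the documents: derivation N = 50; 2,000 independent edges; edge selection at p < 0.01; stability ρ, taken as the within-person correlation between old and new values, the same for edges and outcome; and k of the 24 participants drawn from the derivation sample. There were 1,000 replicates per cell. Entries are mean r, then the two-sided false-positive rate.

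| ρ | k = 0 | k = 3 | k = 6 | k = 12 | k = 24 |
|---|---|---|---|---|---|
| 0.3 | 0.00; 0.04 | 0.00; 0.05 | 0.03; 0.06 | 0.07; 0.06 | 0.14; 0.10 |
| 0.5 | 0.00; 0.05 | 0.06; 0.06 | 0.10; 0.07 | 0.18; 0.13 | 0.33; 0.37 |
| 0.7 | 0.01; 0.05 | 0.08; 0.07 | 0.18; 0.14 | 0.32; 0.35 | 0.55; 0.83 |

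The Monte Carlo standard error is √(0.05 × 0.95/1000) = 0.007 near 0.05 and √(0.35 × 0.65/1000) = 0.015 near 0.35.

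**Step 4: sensitivity to the assumptions.** The next figures are the chance of a significant *positive* r (nominal 2.5%) for k = 0, 3, 6 and 12, with selection at p < 0.05.
- 5,000 independent edges, ρ = 0.6: about 3%, 7%, 23% and 44%.
- 1,000 independent edges, ρ = 0.6: about 3%, 5%, 12% and 30%.
- 1,000 edges, outcome stability lowered to 0.3: about 3%, 3%, 4.5% and 9%.

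The direction is the same throughout, but the size is not: it depends on the number of repeaters, the effective number of edges and the stability of the outcome. With no repeaters the test keeps its nominal level.

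**The case against.** The strongest objection is that the key fact is missing. No section says that the derivation sample came from this provider. By their titles, the references attached to the recruitment sentence are studies of cocaine abstinence and of cocaine-dependent people, not the opioid network study. Same team and same kind of patient do not prove same provider, and same provider does not prove same people. A reader might infer that derivation participants have been or will be re-enrolled; the documents do not support that.

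Re-enrolment also has natural limits. The provider is large and at most about 40 people will be scanned. Recent opioid use and the age limit will rule out some earlier volunteers, and no section describes re-contacting them. Referral of people entering the program points towards newcomers. That last limit is weak, because it applies only when possible, item 9 has clinicians informing patients at regular visits, and three months of treatment is required.

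The simulated rates rest on assumed inputs. Real edges share nodes and are not independent. The outcome is a short run of weekly urines in people selected for current use, so its stability may be low. Overlap of 6 to 12 of 24 has no basis in the text.

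Finally, the replication is one sentence outside Aims 1 to 3. All of this stands, and it limits the point to a safeguard for one analysis. It does not remove the gap: the plan calls the test a replication and does nothing to secure or document independence.

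**Conclusion.** The point holds as a minor one. The replication in item 13 is not restricted to people outside the derivation sample, and nothing in the eligibility rules does that job. If overlap exists, the result would not meet the protocol's own independent-sample standard. If overlap is zero, the test is sound as planned.

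Under the illustrative assumptions the bias is small with a few repeaters. It becomes material only at about 6 to 12 of 24 with moderate to high within-person stability. These figures show direction and scale and are not estimates of this trial's error rate.

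Two further inferences would go too far. The first is that Aims 1 to 3 are biased: Aims 2 and 3 rest mainly on within-person change, Aim 1 concerns opioid use itself, and no effect on any of them has been shown. The second is that earlier participants must be kept out of the trial altogether: only one secondary correlation is exposed, so an analysis-level rule is enough.

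**What to change.** 1. At screening, check each participant against the team's own study keys and record whether their imaging data were used to derive or tune the network.
2. In Section I, item 13, state that the replication correlation is run as primary only in participants not so used, with the all-participant correlation as a sensitivity analysis. Report both sample sizes.
3. Keep derivation-sample members in all other analyses. No new exclusion criterion is needed.

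If the team already knows that overlap is impossible, one sentence saying so settles the matter.

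**Cost.** An identity check per participant, and possibly a smaller n for one correlation. By the formula in the working, the critical |r| rises from 0.404 at n = 24 to 2.093/√(19 + 4.381) = 0.433 if 3 people are set aside, and to 2.120/√(16 + 4.494) = 0.468 if 6 are. The loss is small where the overlap is small. It grows only where the all-participant result would be hardest to interpret.
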